4. STUDY DESIGN

C3FIT is a randomized comparative effectiveness trial (CET) of two care delivery methodologies at approximately 18 clinical sites. Primary and secondary outcomes are described in Section 1.

A. Disease-specific Enrollment Criteria

Clinical Indicators. Definitive stroke will be defined by ICD-10 code criteria. Definitions will be based on ICD-10 criteria (see Table 4). Investigators will use tests and assessments deemed appropriate for an individual patient to determine the appropriate diagnosis. Additional stroke subtype categorization will occur using the TOAST Criteria as performed by C3FIT clinical site investigators.

Prior Therapy. There is no exclusion for prior therapy.

Demographic Characteristics. The clinical sites have been carefully selected with the goal of providing nationwide representation, urban and rural representation, inclusion of both men/women and all race/ethnic groups affected by stroke. Patients aged 18 and older are eligible with no upper age exclusion criterion.

Contraindications. Since no drugs or experimental devices are utilized in this trial there are no specific contraindications.

Pregnancy Exclusions. There is no exclusion for pregnancy or planned lactation and no inherent risk from the proposed intervention.

B. Randomization

C3FIT is randomized at the facility (clinical site) level rather than the individual patient level. Randomization at the facility level is appropriate, as the proposed comparator arms could not be reasonably instituted at the patient level for a system change design. Sites will be stratified by patient volume and geography and randomized to management using the CSC/PSC or ISPU model.

C. Site Selection

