4. STUDY DESIGN

C3FIT is a randomized comparative effectiveness trial (CET) of two care delivery methodologies at approximately 18 clinical sites. Primary and secondary outcomes are described in Section 1.

A. Disease-specific Enrollment Criteria

Clinical Indicators. Definitive stroke will be defined by ICD-10 code criteria. Definitions will be based on ICD-10 criteria (see Table 4). Investigators will use tests and assessments deemed appropriate for an individual patient to determine the appropriate diagnosis. Additional stroke subtype categorization will occur using the TOAST Criteria as performed by C3FIT clinical site investigators.

Prior Therapy. There is no exclusion for prior therapy.

Demographic Characteristics. The clinical sites have been carefully selected with the goal of providing nationwide representation, urban and rural representation, inclusion of both men/women and all race/ethnic groups affected by. Patients aged 18 and older are eligible with no upper age exclusion criterion.

Contraindications. Since no drugs or experimental devices are utilized in this trial there are no specific contraindications.

Pregnancy Exclusions. There is no exclusion for pregnancy or planned lactation and no inherent risk from the proposed intervention.

B. Randomization

C3FIT is randomized at the facility (clinical site) level rather than the individual patient level. Randomization at the facility level is appropriate, as the proposed comparator arms could not be reasonably instituted at the patient level for a system change design. Clinical sites were stratified by geography, balanced by patient volume, and randomized to the CSC/PSC or ISPU model.

C. Site Selection

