## **1. Introduction**

C3FIT is a cluster -randomized clinical trial randomizing 24 sites (21 of which provided data and will be included) to assess the effectiveness, defined at 12-months post-stroke discharge, of post-stroke care delivered using the Joint Commission (JC)-certified Comprehensive or Primary Care (CSC/PSC) model compared to an integrated, coordinated, technology-enabled Integrated Stroke Practice Unit (ISPU) model (that includes CSC/PSC care). The trial has two primary outcomes, the modified Rankin score (mRS) and the Stroke Impact Scale (SIS), both assessed at baseline (for SIS, only in approximately 50% of the participants), and at 3, 6 and 12 months. Any beneficial treatment effect of the ISPU approach on the mRS and SIS is presumed to be through a beneficial effect on “intermediate” factors, specifically better control of: 1) systolic blood pressure (SBP) to levels below 130 mmHg, 2) LDL levels to levels below 70 mg/dL, 3) HbA1c to levels below 7%, 4) smoking cessation, 5) adherence to AHA diet guidelines by following a Mediterranean-type or DASH diet, and 6) adherence to AHA exercise guidelines by a usual exercise level of moderate or above. Each of these intermediate factors will be assessed among those failing to be in control at hospital discharge (i.e., for SBP, among those with discharge SBP $\geq$ 130 mmHg; for LDL, among those with discharge LDL levels above 70 mg/dL, etc.). Because of this presumed pathway for potential effects, the assessment of treatment effects on these six intermediate factors is considered an integral part of the assessment of primary outcomes. Because the cluster-randomization may fail to balance the treatment groups on key factors potentially affecting outcome, treatment differences will be assessed after a series of incremental models, first in a crude model with no adjustment, then with adjustment for measures of stroke severity, then with further adjustment for demographic factors, and then with further adjustment for major cardiovascular risk factors. Treatment differences for both the two primary outcome variables and the six intermediate factors will be assessed using a mixed model approach including the assessments at baseline, 3 months, 6 months and 12 months.

Beyond the intermediate factors above, the study also has secondary outcomes including mortality, recurrent stroke, rehospitalization, time at home, depression, caregiver strain, and perceived support.

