## **2. Definitions and classification of covariates**

The covariates used in the incremental models include measures of stroke severity, demographic factors, and traditional cerebrovascular risk factors.

- Measures of stroke severity
  - Discharge location, classified as discharged home vs. not home (skilled nursing, rehabilitation center, etc.).

- Discharge mRS, categorized as 0, 1, 2, 3 or 4 or more (noting relatively few patients with discharge mRS of 5).
- Discharge NIH Stroke Scale (NIHSS), categorized into approximate quartiles of 0, 1, 2-4 or 5+
- Stroke subtype (hemorrhage vs. infarction)
- Demographic factors
  - Age, considered as a continuous factor
  - Male sex
  - Race/Ethnicity, categorized as non-Hispanic white (NHW) versus not NHW (including both other races and Hispanic participants)
  - A summary neighborhood index of socio-economic status (nSES) based on previously published methods, including six variables representing wealth/income, education and occupation: (1) log of median household income, (2) log of median value of owner-occupied housing units, (3) proportion of households receiving interest, dividend, or net rental income, (4) proportion of adults aged  $\geq 25$  years with a high school diploma, (5) proportion of adults aged  $\geq 25$  years with college degree, and (6) proportion of people employed in executive, managerial or professional occupations.
- Baseline cerebrovascular risk factors
  - Cigarette smoking, categorized as current vs. non-current (past or never)
  - Hypertension as a dichotomous variable
  - Dyslipidemia as a dichotomous variable
  - Diabetes as a dichotomous variable
  - Atrial fibrillation or irregular heartbeat as a dichotomous variable
  - Sedentary activity (defined as a score of 0-No Physical Activity or 1-Sedentary or sitting most of the time)

Because the mixed models will include baseline assessment of the outcome variable (i.e., outcomes include measures at times 0, 3, 6, and 12 months), covariates directly related to the outcome being assessed will be excluded from the model. That is, variables will not be used as both an outcome and as a predictor in the same model. For example, discharge mRS will not be included in the models predicting treatment differences in mRS, and baseline hypertension will not be included in models assessing treatment differences in SBP. Rather, changes from baseline to the 3, 6 and 12-month visits will be assessed using contrast statements.

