### **3. Primary Outcome Analyses**

#### **3.1. Analysis of intermediate factors**

Because the ISPU intervention was targeted to specific groups determined by baseline assessments, the primary analysis of the six intermediate factors will be restricted to the estimation of treatment differences among patients who were not in control at discharge, specifically assessing the percentage of patients with:

- 1) SBP below 130 mmHg at 3, 6, and 12-months among those with SBP of 130 mmHg or above at discharge
- 2) LDL below 70 mg/dL at 3, 6, and 12-months among those with LDL of 70 mg/dL or above at discharge

- 3) HbA1c below 7% at 3, 6, and 12 months among those with HbA1c of 7% or above at discharge
- 4) Smoking cessation at 3, 6, and 12-months among those smoking at dischargement,
- 5) Adhering to a Mediterranean or DASH diet among those not adhering at baseline
- 6) Having regular exercise levels of moderate or above among those with lower levels at baseline.

The primary hypothesis will focus on compliance/adherence at the 12-month visit, but mixed models will be used with assessments at the 3 time points (3, 6, and 12 months) and treatment differences reported at all three follow-up times.

Analyses will generally take the approach of using a mixed model approach with: 1) repeated measures at 3, 6 and 12 months, and 2) a random effect for patient and site (if models do not converge, site will be considered as affixed effect). As all of the intermediate factors will be dichotomized for the follow-up assessments, outcomes will be assessed using PROC GLIMMIX. Treatment differences will be assessed in a series of incremental models: 1) crude, 2) adjusted for stroke severity, 3) further adjustment for demographics, and 4) adjustment for cerebrovascular risk factors (see section 2 for factors in each group). The temporal pattern of treatment differences at 3, 6 and 12-months will be described by the treatment-specific proportion adherent/compliant with 95% confidence intervals. The primary assessment of treatment efficacy will be the p-value and confidence intervals for the treatment difference in the proportion at the 12th months; however, p-values and confidence intervals for months 3 and 6 will also be reported.

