In addition to this primary analysis of the intermediate factors that is restricted to those not compliant/adherent at discharge, a supplemental analysis will assess the proportion compliant at 3, 6, and 12 months regardless of compliance at month 0 (i.e., proportion compliant/adherent in the entire population). This analysis will consider a mixed modeling approach with outcomes at 4 time points (0, 3, 6, and 12 months). The focus of this analysis will be on the change in the proportion compliant between month 0 and 12 months (but also reporting the change in the proportion to 3 and 6 months). In addition to assessing treatment differences in the change in the proportion, the treatment differences in the proportions at the 4 time points will be assessed.

For all six factors, analyses assessing the potential for bias from missingness will be performed using inverse probability weighting (for both the analysis restricted to those not compliant/adherent and for the entire population analysis). This will be conducted by first developing a logistic regression model estimated in all subjects predicting the probability of observing the 12-month observation. Predictors in the model will be site (with cluster randomization, implicitly including treatment effect), age, NHW race/ethnicity, sex, NIHSS and nSES. The inverse of this probability will be standardized by dividing by the sum of the inverses, standardizing the inverse probabilities to have the same sum as the sample size; hence, not inflating or deflating statistical power. The analysis for the factor will then be repeated using the inverse probability weights. Should the interpretation of results differ between the weighted and unweighted analyses, the primary interpretation will be based on the weighted analysis, and the weighted analysis will be the basis for figures and estimates in the manuscript will focus on the weighted results.

Effect modification will be assessed by age, sex, race/ethnicity, stroke sub-type, stroke severity (discharge NIHSS dichotomized at 0 to 1 versus 2+), and nSES.

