### **3.2. Modified Rankin Score (mRS)**

The mRS is a 7-point scale, ranging from 0 (normal) to 6 (dead), where at baseline the scores were from 0 to 5 (discharged dead were excluded from the study). During follow-up, patients were scored a 6 at the 3, 6 and 12-month follow-up if the patient died before the respective follow-up (even if the patient missed intervening visits). The mRS will be dichotomized as “good outcomes” of 0 to 2 points, and “poor outcomes” of 3 to 6 points. Analysis will use a mixed model approach (implemented through GLIMMIX) with the treatment-specific proportion of “good outcomes” modeled at months 0, 3, 6, and 12 (reported with the p-value for treatment differences at each time point). The primary outcome will be treatment differences in the change in the proportion with good outcomes between months 0 and 12, but differences to months 3 and 6 will also be estimated. These differences will be estimated with the same 4-level incremental adjustments, and with both unadjusted and inverse-probability weighted adjustment. Effect modification will be assessed by age, sex, race/ethnicity, stroke sub-type, stroke severity (discharge NIHSS dichotomized at 0 to 1 versus 2+), and nSES. With the discharge mRS as an outcome, the analysis will not be adjusted for baseline mRS.

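### The SAP models site but leaves geography and patient volume, the two factors that restricted the site randomisation, out of every model; comparisons of level at a visit, and time at home, may lose precision as a result

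*Protocol*

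**What the plan says.** The two protocol versions describe the randomisation differently. In section 4B the CSC/PSC version says "Clinical sites were stratified by geography, balanced by patient volume, and randomized to the CSC/PSC or ISPU model". Section 4B of the ISPU version says "Sites will be stratified by patient volume and geography and randomized to management using the CSC/PSC or ISPU model". The Summary of each version repeats its own account. Geography is a stratum in both, but volume is a stratum in one and a balancing factor in the other.

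SAP section 1 describes the trial as "randomizing 24 sites (21 of which provided data and will be included".

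SAP section 2 introduces the covariates: "The covariates used in the incremental models include measures of stroke severity, demographic factors, and traditional cerebrovascular risk factors". The itemised list covers discharge location, mRS and NIHSS, stroke subtype, age, sex, race/ethnicity, a neighbourhood socio-economic index and baseline risk factors. It names no geographic stratum and no site volume, and sections 3 and 4 add neither. The neighbourhood index measures socio-economic status and does not stand in for the stratum.

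Site itself is modelled. Section 3.1 specifies "a random effect for patient and site (if models do not converge, site will be considered as affixed effect", and sections 4.1 and 4.2 also use hierarchical models. Site is a predictor in the missingness weights too, but that model does not put geography or volume into an outcome model.

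The contrasts differ by outcome. For mRS, section 3.2 says "The primary outcome will be treatment differences in the change in the proportion with good outcomes between months 0 and 12", and section 3.3 takes the corresponding change in mean SIS. The six intermediate factors, which section 1 treats as integral to the primary assessment, are judged on the month-12 proportion. Sections 3.2 and 3.3 also report treatment differences at each visit. Caregiver strain and perceived support are compared as levels, and depressive symptoms are handled as an outcome measured only at follow-up.

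**The concern.** An analysis normally carries the factors that restricted its randomisation, or says why not. Treatment here varies only between sites, so a level comparison rests on about 21 site means and its error term is largely between-site. Restricting the allocation on geography and volume limits how far those factors can move the arm difference. A model that omits them still counts their contribution as between-site error, so the reported standard error is larger than it need be and the test is conservative. SAP section 1 itself worries that cluster randomisation may leave the arms unbalanced, yet its remedy uses only patient-level and neighbourhood-level covariates. At stake is power for the level comparisons.

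**Working it through.** **Inputs.** SD of SIS 8; ICC 0.05, with 0.10 as the unfavourable case and 0.01 as the protocol's own expectation (protocol 9A); 18 sites of about 100 as first planned (9A); reduced total of 1,262 (Summary); 21 sites analysed (SAP 1). Assumed because not stated: two-sided alpha 0.05, equal site sizes, a 10/11 split, four geographic strata, and R², the share of between-site variance that geography and volume explain.

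**Step 1: reproduce the plan's figures.** With m patients per site and K1, K2 sites per arm,

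SE = sqrt{[ICC·SD² + (1 − ICC)·SD²/m]·(1/K1 + 1/K2)}, with K1 + K2 − 2 degrees of freedom.

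For 9 + 9 sites of 100 and ICC 0.05: SE = sqrt[(3.2 + 0.608)·(2/9)] = 0.920. Noncentral t on 16 df gives detectable differences of 2.75 (80% power) and 3.18 (90%); the protocol states 2.7 and 3.2. At ICC 0.10 the results are 3.72 and 4.30; the protocol states 3.7 and 4.3. The formula is therefore consistent with the plan's figures, which concern a difference in level.

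**Step 2: the unadjusted level contrast with 21 sites.** m = 1,262/21 = 60.1. At ICC 0.05, SE = sqrt[(3.2 + 60.8/60.1)·(1/10 + 1/11)] = 0.897. With 19 df the detectable difference at 80% power is 2.65. The between-site share of the variance is 0.05·60.1/(0.05·60.1 + 0.95) = 76%. At ICC 0.01 it is 0.01·60.1/(0.01·60.1 + 0.99) = 38%.

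**Step 3: adjust.** Replace ICC·SD² by ICC·SD²·(1 − R²) and spend four df (three for four regions, one for volume), so 19 becomes 15. The df cost alone multiplies the detectable difference by the ratio of (t0.975 + t0.80) at 15 and 19 df, which is 1.015.

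| R² (assumed) | SE, ICC 0.05 | Change in detectable difference, ICC 0.05 | Change, ICC 0.01 |
|---|---|---|---|
| 0 | 0.897 | +1.5% | +1.5% |
| 10% | 0.862 | −2.4% | −0.5% |
| 20% | 0.826 | −6.5% | −2.4% |
| 30% | 0.788 | −11% | −4.4% |
| 50% | 0.706 | −20% | −8.6% |

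Break-even R² is about 4% at ICC 0.05 and about 8% at ICC 0.01. At ICC 0.10 the gains run from 3.0% (R² 10%) to 23.7% (R² 50%).

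**Step 4: direction of the error.** Site means were simulated with stratified allocation of 24 sites in four assumed strata, three sites lost, ICC 0.05 and 20,000 runs. At a true difference of 2.7, power without and with adjustment was 81.4% and 79.6% (R² 0), 82.4% and 86.8% (R² 25%), and 85.2% and 94.5% (R² 50%). Type I error of the unadjusted test was 3.0% at R² 25% and 1.9% at R² 50%.

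**Step 5: the change contrast.** Write the outcome as visit mean + visit-specific treatment effect + g·(site factor) + site intercept + patient intercept + error. The treatment difference in change from month 0 to 12 subtracts two visits at the same site, so g and the site intercept cancel. Generalised least squares for 21 sites of 60, ICC 0.05 and an assumed patient share of 0.4 confirms this. The SE of the SIS change is 0.4733 with or without geography when baseline is complete, and 0.6013 with or without it when half the baselines are missing. If eight sites have no baseline SIS and the other 13 have 80%, it is 0.6094 without and 0.6091 to 0.6087 with geography (R² 25 to 50%), a gain of about 0.1%.

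**The case against.** The strongest reply is that the SAP's primary contrast for both named outcomes is a change from month 0 to 12, where a time-constant site factor buys essentially nothing. That stands for SIS and, approximately, for the logistic mRS model. It does not cover the month-12 proportions of the six intermediate factors, the differences reported at each visit, or the secondary outcomes without a month-0 contrast.

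Second, the gain is not established. The documents give neither R² nor the number of strata, and the protocol expects an ICC nearer 0.01. Models 2 to 4 may already absorb some regional difference through severity, race/ethnicity and neighbourhood socio-economic status, so the relevant R² is what remains after them. This stands; the table is a range, not an estimate.

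Third, blanket adjustment would collide with SAP 4.1, which limits covariates to one per ten events, and with the fixed-site fallback, under which geography and volume are aliased with site. Both points stand and narrow the remedy.

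A reader might also infer that the analysis ignores the randomisation. It does not: the randomised unit is modelled as a random effect, and only the restriction factors are missing. Nor do the documents show that losing three of 24 sites upset the balance; they show only that balance among the remaining 21 is no longer guaranteed by design.

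**Conclusion.** The omission is real and unexplained, and it deserves correction, but it concerns efficiency, not validity. For level comparisons and time at home it tends to make tests conservative once the two factors explain more than about 4% of between-site variance at ICC 0.05, or about 8% at ICC 0.01. The plausible effect of adjusting runs from a 1.5% larger detectable difference to one about 20% smaller at ICC 0.05, or 8.6% smaller at ICC 0.01, for R² between 0 and 50%. This rests on the assumed R², four strata, equal site sizes and a 10/11 split. The figures are for a continuous outcome and are only a proxy for the binary ones.

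Two stronger readings are not supported. The figures must not be quoted for the month 0-to-12 change in SIS or mRS. And the omission does not inflate type I error: in the simulation the unadjusted test fell below its nominal level.

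**What to change.** 1. State one randomisation scheme, in the same words, in the Summary and section 4B of both protocol versions. Whether volume was a stratum or a balancing factor must be settled before the covariates can be named.
2. In SAP 2, 3.1 to 3.3 and 4.2 to 4.5, add the geography stratum actually used (collapsed only if strata are sparse) and site volume (one continuous term) as prespecified fixed effects in all four incremental models, including the crude one, alongside the random site effect.
3. In SAP 4.1, include them only where the ten-events-per-factor rule leaves room, and say where they come in the order of entry.
4. State that both terms drop out wherever the fixed-site fallback is used.
5. If the factors are to stay out, give the reason in the SAP, having regard to the 21 sites.

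The cost is two site-level variables that the randomisation itself required and about four of the 19 between-site degrees of freedom, which is a detectable difference about 1.5% larger if the factors explain nothing.

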5. MODEL OF CARE – THE CSC/PSC ARM

Post-discharge, management and treatment of patients in the CSC/PSC arm will follow general clinical practice guidelines as is usually provided by the site in the management of all patients following a stroke, e.g. one-month clinic follow-up by a vascular neurologist. Patients will return to the CSC/PSC site per protocol for data collection research visits at 3, 6, and 12 months, and the University of Alabama Birmingham (UAB) SDCC Survey Research Unit (SRU) will contact them by phone at these times (see Figure 4). No C3FIT intervention management will be provided at these visits, however, usual standard of stroke care will occur. If there are emergent needs, the patient will be referred to that site's emergency department, patient's family physician, or the physician PI at the site.

